Eligibility Criteria. Inclusion criteria: All Hispanic caregivers of Veterans with a primary diagnosis of stroke are eligible for participation if they meet the following criteria: 1) are the primary caregiver and provide the majority of care for a Veteran who has a diagnosis of stroke (ICD9 codes for stroke: 430-438 or ICD 10 codes 160.0 through 169.998) within the last year and who has at least two activity of daily living (ADL) deficits or a new or worsening neurological problem, 2) have Internet access and ability, (either themselves or via a relative or friend) 3) are reachable by cell or home phone, 4) Spanish is their preferred language, 5) have moderate to severe stress, and 6) self-identify as Hispanic, and 7) agree to random assignment to the intervention or standard care group. We will determine caregiver status.

Previous researchers have found that one individual is typically identified as the primary caregiver and is responsible for the majority of caregiving tasks. [24,56] We will determine time since stroke by reviewing the Veterans' CPRS records. Deficits in activities of daily living [ADL] will be assessed by asking caregivers if the Veteran is unable to complete any of the ADLs on the SIS-16.[59] Caregivers of Veterans who had either embolic or thrombotic strokes are included because there are no previous studies that indicate a differential impact of stroke type on caregiver outcomes. Similar to Grant et al.,[24] we will not limit the study to caregivers of first-time stroke survivors. Studies have found that there is a relatively high incidence of stroke occurrence and that subsequent strokes may be more severe and cause greater stress and depression than first strokes.[30] Stress will be measured by the Perceived Stress Scale. Hispanic/Puerto Rican ethnicity, Internet

access and ability will be determined by caregiver self-report. Exclusion criteria: We will exclude caregivers who are managing end-of-life issues (stroke survivors are likely to die within five months following discharge) Life expectancy will be determined by reviewing the CPRS records and conferring with our physician team members.

Recruitment and enrollment procedures: Recruitment and enrollment procedures are guided by procedures that have been used successfully to enroll caregivers in our pilot project and other caregiver studies.

Recruitment procedures will be implemented during the second half of Q1, year 01, and continue through the end of year 05.

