
James A. Haley Veteran's Hospital site recruitment procedures (these recruitment procedures were approved by the University of South Florida IRB (IRB#: Pro00039920): We will identify potential study participants via clinician referral. Clinicians in the VA will ask Veterans with stroke (ICD9 codes 430.0 -438.00 or ICD10 codes 160.0 -169.98) who are receiving care on their units or facilities and/or their caregivers if they are interested in talking to a research staff member about the study. The VA clinicians who care for Veterans with a stroke are busy and often rotate shifts, so the nurse recruiter will additionally review the VA's computerized record system (CPRS) to identify in-patient Veterans in order to assist the clinicians in locating potential participants. The nurse recruiter will review the minimum amount of information necessary to determine if the Veteran is admitted for new onset stroke. Once a Veteran is identified as having a new onset stroke, the nurse recruiter will notify a VA clinician involved in that Veteran's care either in person, by phone, or through encrypted e-mail. The clinician will then ask the Veteran and/ or caregiver if they are interested in talking to a research staff member about the study. If either the Veteran or caregiver is interested in the study, the nurse recruiter will contact the caregiver and/or Veteran (using contact information found in CPRS or provided by the clinician) to arrange times to meet or talk with the caregiver and Veteran. The nurse recruiter will explain the main study using a brief script and, if interested, obtain written permission for the main study staff in Gainesville or Puerto

Rico to contact the participant via telephone for recruitment. The written permission form will be shared with the main study staff. Participants can self-refer after receiving a referral postcard with study team contact information on it by a clinician or the nurse recruiter. We will request a HIPPA waiver for screening and recruitment.

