**Data collection procedures:** Study personnel will follow a detailed, procedure manual, translated and adapted into Spanish from our previous pilot project, to collect the data. A data collector who is fluent in Spanish and has strong communication skills either in Gainesville or PR will be trained to conduct the assessments. Following enrollment and after going over the written statement script with eligible and interested study participants the data collector will contact caregivers at an agreed upon time to obtain demographic data and administer baseline survey questionnaires (see measures). To facilitate the collection of the baseline assessment, we will mail the demographic data form and questionnaires in advance for caregivers to read while the data collector asks questions and documents the caregivers' responses. We will also review the Veterans CPRS records and document the Veterans' age, gender, race/ethnicity, date/location/type of stroke, number of previous strokes, and resource use and any information related to the Veterans' care (treatments, medicines, patient and family education, case management, etc.). All caregivers who meet the study eligibility

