| Quality of Life – VR-12 RAND 12-Item Health Survey v2 (Spanish Version)                       | The VR-12 is a multi-use, self-administered health survey comprised of 12 items. The instrument is primarily used to measure health related quality of life, to estimate disease burden and to evaluate disease-specific benchmarks with other populations. It uses of five-point response choices for the questions that comprise two scales: "Physical Health Summary Measure" and "Mental Health Summary" Measure". The VR-12 has good psychometric properties.    | <10 minutes |
| Problem Checklist  | This instrument was created for the study. The instrument asks caregivers to indicate what problems they or their Veterans are dealing with.   | <5 minutes  |
| Veteran Measures  |  |             |
| Demographic and Health-related variables   | Age, gender, race/ethnicity, facility from which Veteran received stroke related services (i.e., hospital, community living center, rehabilitation), length of rehabilitation, date/location/type of the stroke, and number of previous strokes will be obtained from CPRS review.   | N/A         |
| Functional Abilities – Stroke Impact Scale (Translated)                                       | The Stroke Impact Scale is comprised of 16 short questions and is used assess physical function of patients with stroke.   | <2 minutes  |

|  |  |            |
|--|--|------------|
| Healthcare Utilization – Unintended hospital bed days of care, number of emergency room visits, number of unscheduled clinic visits | Data on healthcare utilization will be obtained from the CPRS records. We decided to measure healthcare utilization in CPRS rather than obtaining similar data that could be found in the Patient Treatment File (PTF) after communicating with staff in the VA Office of Quality Improvement (OQI). The data collector will record the number, dates, and the reasons for all healthcare visits (hospitalizations, ER, clinic visits). Drs. [name] and [name] will review the RA's notes and through consensus decide on which visits were unintended and unscheduled. | N/A        |
| Cost Data – See Aim #3  | We will obtain the standard cost data from the VA Managerial Cost Accounting System (MCAS) (formerly DSS) National Data Extracts (NDE) (total, nursing, pharmacy, laboratory, etc.) by fixed and variable categories and the VA-fee basis files.   | N/A        |

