**Aim #1 - Hypothesis #1 (primary):** Stroke caregivers who receive the intervention will have less depressive symptoms at 1 and 12 weeks post-intervention compared to stroke caregivers in the standard care group. Our primary endpoint is the caregiver depressive score. The focus of the primary analysis will be to examine the effect of the intervention based on “intention to treat.” Data from all the participants will be part of the primary analyses regardless of actual number of completed sessions. As an exploratory study element, we will assess compliance and attempt to determine its effect on study results. For the primary analysis, the general linear mixed model for repeated measures will be used to model the follow-up depression times (1 and 12 weeks post-intervention), adjusted for baseline scores as fixed effects. Let  $y_{ij}$  be the depression score for person  $i$  at time  $j$ , then basic fixed effects model will be:

$$E(y_{ij}) = \beta_0 + \beta_1 \text{Baseline}_i + \beta_2 \text{Time}_{ij} + \beta_3 \text{Group}_i + \beta_4 \text{Group}_i * \text{Time}_{ij}$$

with covariates for baseline depression (Baseline), time (Time=0 for 1 week, 1 for 12 weeks post-intervention), and group (0 if active control, 1 if intervention). In order to control for possible chance sample imbalances resulting from randomization, the model will include covariates for baseline prognostic factors (e.g., discharge from hospital, community living center, or rehabilitation facility; caregivers’ relationship to Veteran; number of previous strokes among Veterans, etc.), deemed to have significant relationships with response and groupwise imbalances. Thus, analyses will be able to compare the groups on the measure of interest while controlling for these factors. The primary outcome of interest will be the immediate post-intervention effect at 1-week post-intervention with the 12-week post-intervention as a secondary outcome. This will be tested based on linear contrast  $\beta_3 + \beta_4$  at two-sided 0.05 level. All tests will be performed at the  $\alpha=0.05$  significance level. The correlation among observations from the same person will be accounted for through the inclusion of a random person effect into the mixed model analysis.

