**Aim #2 - Hypotheses #2 (secondary):** Stroke caregivers who receive the intervention will have superior outcomes (i.e., less burden, better problem solving skills, greater self-efficacy, and better HRQOL,) at 1 and 12 weeks post-intervention than caregivers in the standard care group. The analysis plan for Hypothesis 2 will closely follow the plan outlined above for Hypothesis 1 for each secondary outcome of interest.

**Aim #3 - Hypotheses #3 (secondary):** Veterans whose caregivers receive the intervention will have better functional abilities at 1 and 12 weeks post-intervention and less healthcare utilization at 12 weeks post-intervention measures compared to Veterans whose caregivers are in the standard care group. Since the score for the Stroke Impact Scale can be treated as a continuous, the analysis plan follows exactly as above in Hypothesis 1. Since the Veteran healthcare utilization measures are count data, the models will be a somewhat different. There will be no baseline covariates added to the model, as they are not applicable to the count measures. Analyses will be conducted for the period following baseline to 12 weeks post-intervention assessments. Generalized linear models for count data (such as Poisson or negative binomial regression models, depending on the presence or absence of over-dispersion) will be employed to determine the group effects on healthcare utilization. Log link functions will be employed on the count data to create the correct distributional data forms. As before, in order to control for possible sample imbalances resulting from randomization, all models will include covariates for prognostic factors deemed to have significant relationships with response and significant groupwise imbalances. Thus, analyses will be able to compare the groups on the measures of interest while controlling for these factors.

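### Time since stroke is recorded for every Veteran but no model names it; fixing it in advance in the SIS-16 model could gain a little precision at almost no cost

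*Combined protocol and SAP*

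**What the plan says.** **Who enters.** Section 6, Eligibility Criteria, requires a stroke diagnosis "within the last year and who has at least two activity of daily living (ADL) deficits" or, in place of the deficits, a neurological problem that is new or getting worse. There is an upper limit of one year and no lower limit. Recurrent stroke is allowed: "we will not limit the study to caregivers of first-time stroke survivors". In the Tampa recruitment procedures, a nurse recruiter looks at in-patient records to "determine if the Veteran is admitted for new onset stroke".

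**What is recorded.** Eligibility Criteria states "We will determine time since stroke by reviewing the" Veteran's chart. Data collection procedures lists "date/location/type of stroke, number of previous strokes, and resource use" among the items abstracted, and the Veteran rows of the Measures table say "date/location/type of the stroke, and number of previous strokes will be obtained from CPRS review".

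**What is modelled.** The Aim #1 mixed model has baseline score, time, group, their interaction and a random person effect. Other baseline prognostic factors are added only when judged both related to the response and imbalanced between groups. The examples are discharge setting, the caregiver's relationship to the Veteran and "number of previous strokes among Veterans", and the list is left open. For function, Aim #3 says "Since the score for the Stroke Impact Scale can be treated as a continuous, the analysis plan follows exactly as above in Hypothesis 1". It then repeats the entry rule for all its models, now asking for significant imbalance. Time since stroke is named in none of them.

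**The concern.** A baseline SIS-16 score records the level of function, not necessarily how fast it is changing. Follow-up runs 21 to 23 weeks from enrolment (9–10 weeks to the first post-test, then 12–13 more). Suppose Veterans at different distances from their stroke change at different rates over that time. The interval would then predict follow-up function beyond what baseline explains, and a model without it would carry avoidable residual variance. That premise is plausible, but the documents neither state nor quantify it.

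At stake is the width of the confidence interval for a secondary outcome. The value is already collected, so even a small gain would be cheap.

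**Working it through.** **1. The plan's own sample size.** Inputs from Sample Size and Power Analysis: CES-D difference 3.1, SD 8.9, 80% power, 5% level (two-sided, from Aim #1), 10% dropout.

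n = 2 × [8.9 × (1.960 + 0.842) / 3.1]² = 129.4, so 130 per group; 130 / 0.9 = 144.4, so 145. The stated figure reproduces. It concerns CES-D; no power or precision target is given for SIS-16. (145 per group makes 290, not the 227 to be enrolled. That is a separate matter; 227 is used below.)

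**2. Number analysed.** 227 × 0.9 = 204.3, or about 102 per arm with 1:1 allocation (assumed).

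**3. Effect of adding the covariate.** Let r be the partial correlation of time since stroke with follow-up SIS-16 given baseline SIS-16. Residual variance is multiplied by (1 − r²). One extra covariate costs a factor of about 1 + 1/(N − 4) = 1 + 1/200 = 1.005. The interval-width ratio is √[(1 − r²) × 1.005]. This treats one follow-up visit as a covariance analysis, an approximation to the two-visit mixed model. Every r is an assumption.

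| r | 1 − r² | × 1.005 | Width ratio | Net change in interval | 204.3/(1 − r²), before cost |
|---|---|---|---|---|---|
| 0 | 1.00 | 1.005 | 1.0025 | 0.25% wider | 204.3 |
| 0.1 | 0.99 | 0.995 | 0.9975 | 0.25% narrower | 206.4 |
| 0.2 | 0.96 | 0.965 | 0.982 | 1.8% narrower | 212.8 |
| 0.3 | 0.91 | 0.915 | 0.956 | 4.4% narrower | 224.5 |

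Break-even is where (1 − r²) × 1.005 = 1, which gives r = √(0.005/1.005), about 0.07.

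As an illustration only, borrow the CES-D standardised effect, 3.1/8.9 = 0.348, since none is given for SIS-16. Power is 70.2% without the covariate and, net of its cost, 70.0%, 70.4%, 71.7% and 74.0% for the four rows.

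**4. Would the entry rule bring the covariate in anyway?** A group imbalance at p < 0.05 occurs in about 5% of randomised trials, so the two conditions together can hold only about that often. A simulation checked this (204 Veterans, 3,000 trials per r, interval uniform, linear effect, baseline slope 0.7, both conditions read as p < 0.05; all assumed).

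- The rule admitted the covariate in 0.2%, 1.6%, 3.4% and 5.2% of trials for r = 0, 0.1, 0.2 and 0.3.
- The ratio of standard errors, with to without the covariate, was 1.002, 0.997, 0.982 and 0.957, matching the table.
- The rule recovers part of the gain. At r = 0.2 the spread of the estimated effect fell by 0.5% under the rule and by 2.1% when the covariate was always included; at r = 0.3 the falls were 1.4% and 4.7%.

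**The case against.** **The list is open, and imbalance is covered.** A reader might infer that a chance imbalance in recovery stage would go unadjusted. The documents do not support that. The stated purpose of the extra covariates is to deal with chance imbalance, and time since stroke is unnamed rather than excluded. If it were significantly imbalanced and related to outcome, the rule could admit it. This part of the objection stands. What remains is the precision forgone in the large majority of trials where the rule would not be triggered.

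**Baseline already does the work.** Baseline SIS-16 is in the model, and discharge setting, if it enters, may absorb more. No passage shows that a useful association is left over. This also stands: a loss of precision is possible, not demonstrated, and is close to nil for r up to about 0.1.

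**Why this variable?** Age, stroke type and stroke location are also recorded, and the underlying weakness is the data-driven entry rule. That is fair. Still, time since stroke has a window of up to a year written into eligibility and is abstracted for that purpose, so naming it is a concrete improvement even if the rule itself is left alone.

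**How wide is the spread?** A reader might infer from the Tampa in-patient screening that some Veterans enter within days of stroke. Clinician approach, written permission, a recruitment call and mailed questionnaires all come before baseline, and no passage gives the actual distribution. An early stage is a fair description; days is not established.

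**Cost.** Calling the change free would go slightly too far. It uses one degree of freedom, and because recurrent strokes are allowed, the index stroke and the functional form must be settled.

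**Conclusion.** The point holds as a minor efficiency improvement for the secondary SIS-16 analysis. Time since stroke can vary from an early stage to about a year, is recorded for every Veteran, is named in no model, and would rarely enter under the plan's rule.

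The size rests on an assumed residual association: about 0.25%, 1.8% or 4.4% narrower intervals for r = 0.1, 0.2 or 0.3, against about 0.25% wider if r = 0. It also assumes 10% dropout from 227, 1:1 allocation, and a functional form that captures the association. The comparison is with a model that never includes the covariate, so the gain over the plan's rule is somewhat smaller.

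Two stronger readings should be resisted. A reader might infer that omission biases the treatment comparison; under randomisation it does not. A reader might also carry the gain over to the utilisation or CES-D analyses. The variance formula is for a linear model and does not transfer to Poisson or negative binomial regression with a log link, and nothing in the documents sizes a gain for caregiver depression.

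**What to change.** Add one line to the Aim #3 analysis plan before outcome data by arm are examined: time from the index stroke to the baseline assessment is a covariate in the SIS-16 mixed model, whatever its observed association with the response or balance between arms.

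Two definitions go with it:

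- **Index stroke:** the qualifying stroke within the last year, with a stated choice if more than one qualifies.
- **Functional form:** fixed in advance, for example log-months.

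No new data are needed. The cost is the added line and one degree of freedom. Using the same covariate in the CES-D or utilisation models is optional, for example to keep one common covariate set.

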Recruitment calls will be made to potential participants identified from either of the three sites through the procedures described above by trained, Spanish speaking study staff in either Gainesville or PR. In addition to explaining study purpose and procedures, during the recruitment phone calls we will screen potential participants for study eligibility. Since all study procedures (except clinicians who will ask in person to potential participants if they would like to receive a call to obtain more information about our study) will be conducted over the telephone, we will request a Waiver Documentation of Informed Consent for this study. However, we will utilize an Informed Consent written statement to inform interested and eligible participants about the purpose of the study, study procedures including that some sessions may be recorded, risks, volunteer nature of their participation, potential benefits, who to contact in case of questions or concerns, etc. The written statement will also be used to inform and obtain oral permission to record the interventions. Since we will be requesting a Waiver Documentation of Informed Consent, we will also request a Waiver of master List of Consent and Re-consent. We will track the reasons for caregivers who decline to participate; no patient identifiable data will be collected for this purpose. We will recruit participants for 36 months and anticipate enrolling 8 caregivers per month. Even though we have strict eligibility criteria (see above), we expect that at least 10% of the potential caregivers will be willing to participate and meet our eligibility criteria. To collect Veteran healthcare utilization data, we will request a full waiver of consent to conduct the chart reviews.

**Randomization:** Following baseline assessments, participants will be randomly assigned to one of the two arms. The randomization will be blocked to ensure balanced group membership across time. The block size will be determined by the statistician and will not be shared with the rest of the team. The statistician will develop the randomization scheme and share it with a research staff member. The research staff member will prepare opaque randomization envelopes and provide them to the project coordinator (PC). The interventionist will call the PC when a caregiver is enrolled to obtain the caregiver's group assignment.

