criteria and who are still willing to participate after completing the baseline assessment will be randomized to the intervention group or standard care group. All participants will complete two post-tests; post 1 will occur at approximately 9-10 weeks after enrollment (or 1-2 weeks after completion of the intervention for participants in the intervention group), and post 2 will occur approximately 12-13 weeks after post-test 1. The post-test assessments will include the same tools used in the baseline data collection. In addition, at both post-tests we will ask caregivers to disclose any resources they may have used during the duration of the study. At the 12 week post-test assessment the data collector will also ask questions on the Bakas “Enactment” tool to obtain data concerning the caregivers’ perceptions of the intervention. The data collector, who will be blinded to the group assignment of the caregivers, will telephone the caregivers to obtain the post-test assessments. We will obtain data on healthcare utilization since baseline assessment from the MCAS the Decision Support System National Data Extracts (DSS NDE) and the Non-VA Medical Carefee-basis files. Team members abstracting data from CPRS will be trained and inter-rater reliability testing will be conducted for all data collectors. We will conduct the assessments and intervention sessions at times that are convenient to the caregivers. All caregivers will receive reimbursement for their participation in the study.

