### Intervention

Participants in the intervention group will participate in 8 weekly telephone sessions with an interventionist. The telephone-based intervention consists of a problem-solving telephone support educational intervention led by a trained interventionist. The intervention’s main objective is to reduce caregiver burden and depressive symptoms by teaching caregivers a creative and optimistic approach to solving caregiving related problems. The intervention will utilize the problem solving module and refer to additional information/tools on the Spanish RESCUE website (<http://www.cidrr8.research.va.gov/rescue-espanol/>). The information included in the intervention consists of: 1. Introduction, 2. Illustrative Example, 3. Individualized Practice Exercise, and 4. Summary.

The intervention is adapted from the intervention used in our previous pilot project and based on the work of Bakas et al.,[23] who conducted a successful 8-week telephone intervention which used support approach and a task skill-building kit (TASK). In this proposed project we will tailor our pilot intervention to be culturally relevant for a Puerto Rican population. The intervention was developed to reflect specific characteristics of the target population such as language, cultural values and norms, and degree of acculturation. To enhance the cultural relevance of the intervention, we will use findings from our previous projects and guidelines from authoritative sources [55] that recommend: 1) involving persons from the target population in all phases of the project (e.g., Advisory Consortium), 2) emphasizing themes that are valued by the PR culture (e.g., family, religion, self-reliance), 3) assuring that the language and wording of on-line information is low-literate and appropriate by enlisting services of certified translators and Spanish-speaking experts, and 4) conducting the intervention and assessments by hiring research staff members (i.e., interventionist, data collector) who are Hispanic, fluent in Spanish, and knowledgeable about the PR culture. Research consistently shows that matching interventions to the individual needs of participants is more effective in engaging adults and modifying behaviors than prescriptive approaches.,[16] Other studies underscore the benefits of interventions and programs that are tailored to a specific race/ethnic populations.[55]

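### Post-test 1 has a second, completion-based date in the intervention arm, so late starts or delayed sessions can put the two arms' outcome assessments at different elapsed times

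*Combined protocol and SAP*

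**What the plan says.** All statements below are in section 6, Research Plan.

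- **Data collection procedures.** Every participant has two post-tests. Post-test 1 is dated at approximately "9-10 weeks after enrollment (or 1-2 weeks after completion of the intervention for participants in the intervention group". This is a general rule from enrolment with, in the parenthesis, a second rule for the intervention group. The next assessment is chained to the first: "post 2 will occur approximately 12-13 weeks after post-test 1". On scheduling: "We will conduct the assessments and intervention sessions at times that are convenient to the caregivers". No assessment window and no maximum length of the intervention are given.
- **Intervention.** "Participants in the intervention group will participate in 8 weekly telephone sessions with an interventionist".
- **Randomization.** "Following baseline assessments, participants will be randomly assigned to one of the two arms". Baseline assessment and randomisation therefore both come between enrolment and session 1.
- **Topical Content table, session 1.** The workbook, mailed in advance to intervention caregivers, holds a calendar of agreed dates for the sessions and for the post-test. The table does not say whether the post-test date stands if sessions are rescheduled.
- **Data Analysis, Aim #1 - Hypothesis #1.** The 1-week post-intervention effect is the primary outcome and the 12-week effect is secondary. Time enters the model as 0 or 1. On incomplete delivery: "Data from all the participants will be part of the primary analyses regardless of actual number of completed sessions".

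**The concern.** A randomised comparison of a symptom score should measure both arms at the same elapsed time. Here the intervention arm has a date that depends on when its sessions end, and standard care has no such event. If sessions end late and the completion rule is followed, the arms are compared at different distances from enrolment. Any natural change in CES-D over the extra weeks is then counted as part of the treatment effect.

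Some change over time is plausible. Eligibility takes in strokes up to a year old and requires moderate to severe caregiver stress, and the Tampa procedures look for inpatients with new-onset stroke. What is at stake is a clean reading of the primary endpoint and of the 12-week endpoint that follows from it. The plan also does not say explicitly when a caregiver who stops sessions early is to be assessed, although the primary analysis keeps that person.

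**Working it through.** **Inputs from the plan:** 8 weekly sessions; post-test 1 at 9-10 weeks from enrolment, or 1-2 weeks after completion; post-test 2 at 12-13 weeks after post-test 1; planning effect 3.1 CES-D points (Sample Size and Power Analysis).

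**Step 1. The plan's own figure.** An 8-week programme plus 1-2 weeks gives 8 + 1 = 9 to 8 + 2 = 10 weeks. This matches the stated 9-10 weeks, so the two rules were evidently meant to coincide.

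**Step 2. When they coincide.** Let s be the weeks from enrolment to session 1 and D the total weeks of session delay. Eight weekly sessions span 7 weeks, so session 8 is at s + 7 + D.

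- Intervention post-test 1 under the completion rule: s + 8 + D to s + 9 + D.
- Standard care post-test 1: 9 to 10.
- Gap: (s + 8 + D) - 9 = s + D - 1.

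With no delay the gap is zero only at s = 1. Starting at s = 0 gives -1 week, and s = 2 gives +1 week.

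**Step 3. Effect of delay, with s = 1.** Standard care post-test 2 is at 9 + 12 = 21 to 10 + 13 = 23 weeks. The values of D are assumptions.

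| Assumed D (weeks) | Intervention post-test 1 | Standard care post-test 1 | Intervention post-test 2 | Standard care post-test 2 | Gap (weeks) |
|---|---|---|---|---|---|
| 0 | 9-10 | 9-10 | 21-23 | 21-23 | 0 |
| 2 | 11-12 | 9-10 | 23-25 | 21-23 | 2 |
| 4 | 13-14 | 9-10 | 25-27 | 21-23 | 4 |
| 6 | 15-16 | 9-10 | 27-29 | 21-23 | 6 |

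**Step 4. Does the model absorb it?** No. Time = 0 labels post-test 1 and Time = 1 labels post-test 2, whatever the actual week. The group difference is beta3 at Time = 0 and beta3 + beta4 at Time = 1. Both are exposed, so the point holds whichever of the two is tested as primary.

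**Step 5. Size of bias.** Bias = average gap x weekly drift in CES-D. The documents give neither term. Purely as illustration, an assumed average gap of 2-4 weeks and an assumed drift of 0.1-0.3 points per week give 2 x 0.1 = 0.2 to 4 x 0.3 = 1.2 points. That is 0.2/3.1 = 6% to 1.2/3.1 = 39% of the planning effect. The upper end is demanding: 0.3 points per week over 9.5 weeks is 2.85 points of change in standard care alone, close to the whole planning effect.

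**The case against.** The strongest reply is that the enrolment rule covers all participants and the parenthesis only restates it for an on-schedule programme. Step 1 supports that as the intention. The wording nevertheless offers the intervention group an alternative, and the plan does not say which rule governs when the two differ.

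A second reply is the workbook calendar, which gives intervention caregivers an agreed post-test date before session 1. This weakens any claim that every slipped week must move the assessment. It does not settle the matter, because nothing says the date is held if sessions move.

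Third, the convenience sentence covers assessments in both arms, so it does not show that only the intervention arm can drift. That is fair. It allows flexibility in both arms, but only the intervention arm has an anchor that moves with its sessions.

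A reader might also infer that caregivers who stop early have no assessment date and would be lost from one arm. The documents do not support that: all participants are to complete both post-tests, the 9-10 week rule is the natural fallback, and the primary analysis keeps everyone. What is missing is an explicit statement.

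Finally, anchoring to completion serves the stated aim of measuring the effect 1 week after the intervention. That aim is legitimate, but it has no counterpart in standard care except through elapsed time.

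**Conclusion.** The point stands as a scheduling weakness that depends on delivery. With session 1 about a week after enrolment and no slippage, there is no gap. With delay, and if the completion rule is followed, the intervention arm is assessed s + D - 1 weeks later than standard care at both post-tests, and the planned model does not correct for it.

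A reader might infer a known bias of some percentage of the 3.1-point effect, or a bias in favour of the intervention. The documents support neither. The 6-39% illustration rests wholly on assumed slippage and drift. The direction depends on whether symptoms ease (later assessment then flatters the intervention) or worsen (it then counts against it). The case for change is that an avoidable asymmetry sits on the primary endpoint and can be removed cheaply, not that a particular error has been shown.

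**What to change.** - Replace the completion-based parenthesis with one schedule for both arms. Date post-test 1 and post-test 2 each at a fixed time from randomisation, for example about 10 and 22 weeks, with the same window.
- State that these dates hold whether or not sessions are finished, which also settles the date for caregivers who stop early.
- State that the post-test date in the workbook calendar follows this schedule.
- Report actual weeks from randomisation to each assessment, by arm.
- Do not adjust for actual weeks except in a clearly labelled exploratory analysis. It is a post-randomisation variable that adherence can affect, so adjusting for it can itself introduce bias.

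**Cost.** Wording and scheduling only; the sample size does not change. Some slow intervention participants will be assessed before their last session, which slightly dilutes the effect. With post-test 1 at 10 weeks from randomisation and sessions spanning 7 weeks, this happens only when start lag plus slippage exceeds 10 - 7 = 3 weeks.
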